A second study (CoolXenon2) has also been successfully undertaken. This study initially was for 24 babies, 12 in each group. One main aim was to establish if we could recruit sufficient neonates within the 5h time limit from birth to Xenon. During this period, when Xe was started only after arrival in Bristol, we lost approximately 40% of potential recruits due to not being able to meet this ambitious time limit. After starting to run the Xe delivery system in the dedicated retrieval ambulance, we applied for an extension to the CoolXe2 study to evaluate the impact on recruitment this would have (8 additional patients, 4 per group) and from that point we have had no missed recruitment due to the 5h time interval.

The CoolXenon2 study revealed an unknown and unforeseen effect of Xenon; Xenon in itself depresses the aEEG trace during delivery which means it is unreliable as an early outcome predictor until the treatment has finished which will for most infants say ≥ 25 h of age (5h old when starting xe +18h treatment + at least 1h recovery). We observed that Xenon depresses seizure activity *per se* (SPR abstract 2013, Appendix 4) and we observed that if Xenon was stopped very fast

Neonatal Xenon Breathing Device: CoolXenon3 Study	Protocol	CI/2013/4414
	Version	Issue 2, Revision 3
	Issue Date	18 Sept 2019
	Page	20 of 79

seizures could occur on stopping Xenon. This means that there is a period where “time to recovery of normal trace” may or may not be affected by Xenon. These data illustrate the importance of examining a small dataset like CoolXenon2 when a new treatment is administered. This means that when analysed the traditional way, aEEG is not reliable as an outcome predictor during the whole of the Xenon administration periods and a few hours afterwards. Since we cannot quantify the aEEG response we do not have a validated early outcome predictor from which we can make a power calculation.

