Therefore, in CoolXenon3 we will record all the same data as in CoolXenon2 and we will use Bayley III converted to Bayley II as appropriate.¹¹ The Bayley clinical neurodevelopmental examination at 18months of age is the primary outcome measure. In the standard treatment, all cooled babies currently undergo MRI brain assessment between 7-10 days of life to confirm the diagnosis of HIE by demonstrating the brain lesions consistent with hypoxia-ischaemia and to prognosticate long-term outcome for parents. In routine clinical practice, some of the cooled babies undergo MRI brain examination around 48 hours of life, when there are concerns of poor recovery of aEEG and abnormal neurology to estimate the severity of brain injury. Undertaking MRI brain assessment around 48 hours of age for all babies during cooling in both cooling and xenon+cooling arms of the study (after completion of xenon) will offer valuable data including early predictors of long-term outcome, assessing the severity of brain injury and progression of brain injury and early effect of xenon on brain injury. Our team is very experienced in looking after the cooled babies during transport and MRI examination. Other putative short-term predictors will continue to be recorded as secondary outcomes. With this enhanced dataset we will be able to validate any early predictors in infants cooled early with or without added Xenon.

There have been no technical problems due to the breathing system, use of the Xenon gas, nor any adverse effects related to these in any of the human studies we have conducted to date.

The safety of Xenon for the immature brain has been demonstrated by no increase in apoptosis³⁰ after 24 hours of breathing the gas in a neonatal piglet model; in comparison breathing isoflurane for the same duration resulted in a 10x increase in apoptotic cell death

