3.3 Secondary Endpoint

The following potential predictors of outcome will be used:

- a. Time to recovery after birth of a normal aEEG¹
- b. MRI scan around 48hours and around day 7 of life, to assess lesions consistent with hypoxic-ischaemia,² absolute quantification of thalamic NAA and white matter fractional anisotropy using tract based spatial statistics.^{3,4,35}
- c. Peak LDH value within 72h of life^{5,36}
- d. Resistance Index (RI).

We will also collect data on:

- e. Plasma glucose at birth (in cord blood)
- f. Age in hours after birth when plasma lactate has fallen to 5mmol/L
- g. Different inotropic drugs needed and the total duration in hours of any inotropic support

Neonatal Xenon Breathing Device: CoolXenon3 Study	Protocol	CI/2013/4414
	Version	Issue 2, Revision 3
	Issue Date	18 Sept 2019
	Page	21 of 79

- h. Number of anticonvulsants given
- i. Amount and duration of sedation (e.g. plasma morphine level), stress level (plasma, salivary, urine cortisol level and adrenocorticotropic hormone)
- j. Age at full oral feeds (breast or bottle or tube)
- k. Neonatal hearing screening result before 14 days of life
- l. Clinical examination at birth, at 7 days of age and at discharge including weight and head circumference

Neurodevelopmental follow up is a part of the routine follow up of infants with HIE, Bayley III examination at 18 months of age.

Disability will be defined as any of:

- m. Bayley III Cognitive Composite score less than 85.¹¹
- n. Bayley III Motor Composite score less than 85 (Bayley scores will also be expressed as a Developmental Quotient (DQ) calculated from developmental age scores as this allows a larger range of scores for those functioning at a low level)³⁷
- o. Bilateral cortical visual impairments
- p. Hearing loss needing amplification > 40dB.

In addition any Adverse Events will be recorded and criteria have been devised for stopping the study early if necessary. The IDRG will review data when 8, 16 and 24 infants have undergone Xenon treatment.

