At the end of the prescribed period of Xe delivery the tracheal tube would be reconnected directly to the mechanical ventilator and normal ventilation and gas mixtures set as clinically appropriate. The cuff of the tracheal tube would be deflated. This tracheal tube would be replaced with an uncuffed tube at a later timepoint as clinically indicated or kept until the patient was extubated after rewarming. Cooling regimes last for 72hrs before slow rewarming commences (0.1-0.4°C per hour). The standard cooling protocol would continue for many more hours after cessation of the additional Xenon regime.

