4.7.2 Potential risks from breathing system

We are using the same breathing circuit to deliver this gas as in previous MHRA approved studies; CoolXenon and CoolXenon2 (MHRA study references CI/2009/0043, CI/2011/0061 respectively). This has been developed over many years by a Consultant Anaesthetist who is a co-researcher on this team and world leader on this subject. Prior to use in these human studies, it has been tested extensively in laboratory neonatal pig simulations of the condition (see section 4.3.1).

To minimise risk of any technical problems:

- a. The equipment meets all necessary international medical device safety and quality standards. It has been professionally constructed using medical grade materials.
- b. The design is such that the Xenon system is placed between the standard mechanical ventilator and the baby. This means that if there is any technical problem, the ventilator can be immediately connected directly to the baby and the Xenon system removed in one simple intuitive operation.
- c. The gas composition, in particular oxygen, of the circuit gas will be continuously measured, as will Xenon and the ETCO₂ (which reflects the arterial value).
- d. The breathing system has an overpressure release valve in the event of any mishap.
- e. Furthermore, if there were any problem due to the Xenon gas itself, reconnection directly to the ventilator would also allow all the Xenon to be breathed out from the baby within a few breaths, i.e. the Xenon treatment is rapidly reversible.
- f. The Xenon will be delivered by trained personnel who have also been involved with laboratory trials using Xenon in animal models and previous MHRA approved clinical trials involving the device.
- g. The possibility of interaction between the Xenon gas and the materials of the breathing circuit has been considered. As Xenon is chemically “inert” i.e. does not form chemical compounds except in the most extreme circumstances, there is no perceived risk.
- h. A full risk assessment in accordance with standard medical device regulatory requirements has been undertaken and thoroughly documented.
- i. The device meets all of the Essential Requirement of the EU Medical Device Directives, with the exception of those being evaluated in the study.

This design of breathing system has now been evaluated in two MHRA approved studies with this patient population. Summary data from the CoolXenon2 study:

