9.0 Assessment of Safety

9.1 Data Review Group

An IDRG will be set up and appropriately constituted with clearly defined terms of reference. Their role will be to independently review the safety of the study after every 8th Xenon patient has been recruited and in the light of this make appropriate recommendations to the study team.

The IDRG will also meet in the event of a death, regardless of cause. This meeting will take place within ~14 days of the death and recruitment into the study will continue in the meantime. This meeting could be in person or take the form of a teleconference. In our initial study of Xenon+cooling a partial external committee met at intervals of every other baby enrolled. For the CoolXenon2 study, the IDRG met after every 4th Xenon patient had been recruited.

In the CoolXenon1 or CoolXenon2 studies there were no significant physiological or biochemical changes or other problems attributable to the Xenon gas or the use of the NXBD. An identical NXBD will be used in this study.

Given the excellent safety record of the previous two studies involving Xenon use and the NXBD, it is considered appropriate that for this study the IDMG should meet after every 8th Xenon patient is recruited.

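### The protocol reports seizures when Xenon is stopped very fast, but its safety statements, risk section and end-of-Xenon text take no account of this, and no seizure outcome isolates the period after stopping

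*Protocol*

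**What the plan says.** **The observation.** Section 2.3, reporting CoolXenon2, says that Xenon depresses seizure activity. It goes on, in a sentence split by a page break: "we observed that if Xenon was stopped very fast" "seizures could occur on stopping Xenon". It gives no count or denominator and does not define how fast is very fast.

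**The safety statements.** Later in the same section: "There have been no technical problems due to the breathing system, use of the Xenon gas, nor any adverse effects related to these", said of all the group's human studies. Section 2.1 says much the same. Section 9.1 says that in CoolXenon1 and CoolXenon2 "there were no significant physiological or biochemical changes or other problems attributable to the Xenon gas" or the device, and section 5.3.2 repeats it. Section 9.1 then cites the safety record of those two studies as the reason for the Independent Data Review Group (IDRG) to meet after every 8th Xenon infant. In CoolXenon2 it met after every 4th.

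**How Xenon ends.** After the list in section 4.6.1: "At the end of the prescribed period of Xe delivery the tracheal tube would be reconnected directly to the mechanical ventilator". Section 4.7.2 says of a problem with the gas that "reconnection directly to the ventilator would also allow all the Xenon to be breathed out from the baby within a few breaths", and section 4.7.1 describes elimination in the same way. On parental withdrawal, sections 4.2.1, 6.1 and 8.1 have Xenon stopped in minutes, as soon as medically safe.

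**The outcomes.** Endpoint 12 (section 3.4) records aEEG/EEG evidence of seizures and anticonvulsant treatment before, during and after Xenon, up to 12 h after cooling ends. Section 3.3 item h is "Number of anticonvulsants given"; sections 4.9.2 and 8.5.4.2 count these drugs over the whole neonatal intensive care stay.

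**The concern.** The protocol describes an effect seen on stopping the study treatment and then writes its safety case as if nothing had been seen. Three things follow.

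- Anyone who relies on the risk section (4.7.1) or on section 9.1 does not meet the observation. Rapid removal of Xenon appears there only as a safety advantage.
- The argument for less frequent IDRG review rests on a statement that another section contradicts.
- Xenon can suppress seizures while it is given, and seizures may appear when it stops. An arm comparison of seizures or anticonvulsants is therefore hard to interpret unless the time just after stopping can be looked at separately and set against the same ages in controls. The protocol defines no such window.

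**Working it through.** There is no stated figure to reproduce, because the protocol gives no seizure rate after stopping. The check is a comparison of sections, plus two short sums from the protocol's own numbers.

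**1. Observation against safety statements.** The observation in section 2.3 concerns CoolXenon2. The statements in 2.1 and 2.3 cover all human studies to date, and those in 5.3.2 and 9.1 name CoolXenon2. They cover the same study. Section 4.7.1 deals with heart rate, gas density, gas-filled cavities and sedation, but not with seizures on stopping. The list of typical problems in 4.6.1 does not mention them, and the numerical stopping rule in 9.3.2 counts deaths only.

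**2. Observation against the stopping text.** Section 2.3 warns about very fast stopping. Section 4.6 ends delivery by direct reconnection. Section 4.7.2 says that direct reconnection clears Xenon in a few breaths, although it says so when describing reversal after a problem. No section shown states the Xenon concentration at reconnection, gives a rate of reduction or refers back to section 2.3. A reader cannot tell whether the routine step is the situation that section 2.3 warns about.

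**3. Review interval.** Planned Xenon infants: 26 (section 4.10).
- Every 8th: 26 / 8 = 3.25, so 3 reviews (at 8, 16 and 24, as section 3.3 says).
- Every 4th: 26 / 4 = 6.5, so 6 reviews.

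The interval justified by the clean record halves the number of scheduled reviews.

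**4. Length of the Endpoint 12 period after Xenon, at the latest permitted times.**
- Xenon starts by 5 h of age and lasts 18 h: 5 + 18 = 23 h of age at the end.
- Cooling starts by 3 h and lasts 72 h; recording runs 12 h beyond: 3 + 72 + 12 = 87 h of age.
- Period after Xenon: 87 − 23 = 64 h.

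The protocol gives no duration for a stopping effect. If 1 to 6 h is assumed, that is 1/64 = 1.6% to 6/64 = 9.4% of the period. A single total for the time after Xenon would mix such seizures with all later ones.

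**5. Controls.** Section 3.4 records the same variables in both groups, but before, during and after are defined by Xenon administration, which controls do not receive. No equivalent ages are stated. The data would support a matched window: section 8.5.4.1 continues aEEG to 82 h in cooled-only infants, well beyond 23 + 6 = 29 h.

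**The case against.** The best defence is that the outcome data are better than they may first appear. Endpoint 12 already separates the time during Xenon from the time after it, for both seizures and anticonvulsants. Section 4.9.1 adds seizure occurrence and duration from continuous aEEG, and section 8.4.3 records each drug with its start date and indication. A narrower window is a tabulation that a statistical analysis plan, not shown here, could supply. This stands: a reader might infer that the signal is pooled away in Endpoint 12, and the text does not support that. Only the anticonvulsant count covers the whole stay.

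Other stronger readings also fail.

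- *That seizures on stopping count as brain injury, or suppressed ones as benefit.* Nothing says so. Endpoint 12 is tertiary and among the safety variables, the analysis is descriptive, and the protocol itself warns that aEEG is unreliable during Xenon and for some hours afterwards.
- *That the IDRG is not shown these seizures.* This cannot be known. Its terms of reference are not shown, and text between 9.1 and 9.3.1 is absent from the copy reviewed. The group also reviews all serious adverse events.
- *That Xenon provokes the seizures.* The observation fits equally well with seizures of the underlying condition becoming visible once suppression ends.
- *That the protocol requires what it warns against.* The warning is conditional and the rate of reduction is unstated. The fault is silence on the point.
- *That the effect on anticonvulsant use can be sized from CoolXenon2.* There, 9 of 14 Xenon and 8 of 14 control infants received anticonvulsants, a difference of one infant, and the 9 may already include cases after stopping.

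None of this removes the conflict between section 2.3 and the safety statements, the omission from 4.7.1, or the use made of the record in 9.1. Those are statements in the protocol that an analysis plan cannot correct.

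**Conclusion.** The concern holds as an internal contradiction with a modest gap in outcome definition. The seizure observation conflicts with statements in four sections (2.1, 2.3, 5.3.2, 9.1), is missing from the Xenon risks, and is not weighed where the IDRG interval is set. The text on ending Xenon is not reconciled with it. No outcome isolates the time just after Xenon ends, and no control window is stated.

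The exposure is every infant who completes Xenon (up to 26) and any who stop early. The size of the effect is unknown, and its cause is not established. The 64 h figure assumes the latest permitted start times; the 1 to 6 h window is illustrative. The primary outcome, the sample size and the mortality rule are not affected, so this ranks below the faults that must be cured before the trial can be interpreted. It bears on infant safety and is cheap to put right.

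**What to change.** 1. Correct the safety statements in sections 2.1, 2.3, 5.3.2 and 9.1 so that they acknowledge the CoolXenon2 observation, with the number of infants affected if known. Add it to section 4.7.1.
2. In section 9.1, justify the every-8th interval in the light of that observation.
3. Reconcile section 2.3 with the end-of-delivery text in 4.6, the elimination text in 4.7.1 and 4.7.2, and the withdrawal text in 4.2.1, 6.1 and 8.1. How Xenon is ended is for the clinical team to decide.
4. State in advance a window after Xenon ends and the same age window in cooled-only infants. From the aEEG and drug data already collected, tabulate seizures and newly started anticonvulsants in that window by arm, apart from the whole-stay anticonvulsant count, and show the table to the IDRG.

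The cost is protocol wording, one extra table and a slightly less favourable stated safety record. No new measurements are needed.

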3.0 Objectives

The aim of this study is to examine the potential neuroprotective effects of the cooling+xenon combination when compared to cooling alone.

3.1 Primary Objective

Our hypothesis is that the Bayley Scales of Infant and Toddler Development (Bayley III) scores at 18m of age will show a trend towards an enhanced neuroprotective effect of the Xenon-cooling combination over cooling alone.

3.2 Primary Endpoint

This is a randomised two group pilot outcomes study comparing Bayley scores between;

- 1) Xenon inhalation for 18 hours in combination with whole body cooling to 33.5 °C for 3 days, and
- 2) the established treatment of cooling the body down to 33.5 °C for 3 days.

This will be applied in term newborn babies who display signs indicating moderate or severe brain injury following poor condition at birth.

3.3 Secondary Endpoint

The following potential predictors of outcome will be used:

- a. Time to recovery after birth of a normal aEEG¹
- b. MRI scan around 48hours and around day 7 of life, to assess lesions consistent with hypoxic-ischaemia,² absolute quantification of thalamic NAA and white matter fractional anisotropy using tract based spatial statistics.^{3,4,35}
- c. Peak LDH value within 72h of life^{5,36}
- d. Resistance Index (RI).

We will also collect data on:

- e. Plasma glucose at birth (in cord blood)
- f. Age in hours after birth when plasma lactate has fallen to 5mmol/L
- g. Different inotropic drugs needed and the total duration in hours of any inotropic support

Neonatal Xenon Breathing Device: CoolXenon3 Study	Protocol	CI/2013/4414
	Version	Issue 2, Revision 3
	Issue Date	18 Sept 2019
	Page	21 of 79

- h. Number of anticonvulsants given
- i. Amount and duration of sedation (e.g. plasma morphine level), stress level (plasma, salivary, urine cortisol level and adrenocorticotropic hormone)
- j. Age at full oral feeds (breast or bottle or tube)
- k. Neonatal hearing screening result before 14 days of life
- l. Clinical examination at birth, at 7 days of age and at discharge including weight and head circumference

Neurodevelopmental follow up is a part of the routine follow up of infants with HIE, Bayley III examination at 18 months of age.

Disability will be defined as any of:

- m. Bayley III Cognitive Composite score less than 85.¹¹
- n. Bayley III Motor Composite score less than 85 (Bayley scores will also be expressed as a Developmental Quotient (DQ) calculated from developmental age scores as this allows a larger range of scores for those functioning at a low level)³⁷
- o. Bilateral cortical visual impairments
- p. Hearing loss needing amplification > 40dB.

In addition any Adverse Events will be recorded and criteria have been devised for stopping the study early if necessary. The IDRG will review data when 8, 16 and 24 infants have undergone Xenon treatment.

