1.0 Overview

This is a prospective randomised pilot outcomes study to be undertaken at St Michael's Hospital, Bristol and Hammersmith Hospital, London. A short delay for recruitment is included to optimise the effectiveness of hypothermia (cooling, HT) and potentially Xenon. Cooled infants that are ≤ 3 h old and start Xenon within ≤ 5 h of age can be accepted into the study. In an experimental study, adding xenon with HT when both were commenced 5 hours after the insult did not provide any additional neuroprotection compared to HT alone⁷; however, 2h delayed Xenon when HT was started immediately was more effective than HT alone.⁸ With the Xenon delivery system mounted in the ambulance we can start the Xe treatment in the local hospital and continue treatment during transport, thus starting Xe within 5h after birth. Since $>90\%$ of patients are retrievals from regional units within the network, the ability to reliably recruit to xenon within the 5h limit is now possible and has been demonstrated as one of the findings of the CoolXenon2 study. Preliminary data from the CoolXenon2 study show that the groups were well balanced with respect to severity of HI. Time to recovery of normal EEG trace is the best single early predictor of outcome¹ and is monitored in all infants. In CoolXenon2 we have found that this does not function as an early predictor as xenon suppresses the aEEG for the entire 18h period of xenon administration and for a short period afterwards. This means that analysed the traditional way, aEEG is not reliable as an outcome predictor during the whole of the Xenon administration periods and a few hours afterwards. Mortality was low, 7% in each group.

In CoolXenon 1 we demonstrated that it is technically feasible to deliver xenon in this patient group without adverse effects on physiology and in CoolXenon2 preliminary analyses we have found that i) Early recruitment losses due to the short birth to treatment-start time limits we have set were then successfully minimised by commencing xenon during retrieval, ii) As in CoolXenon1 there are no adverse physiological effects of giving xenon in this patient group and iii) one planned predictive early marker of outcome, aEEG, has not functioned as expected.

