4.9.3.1 Additional follow up

We will do both short-term (14 days) and long-term (18 months survival) follow-up. In cooled babies we have shown that short-term predictors such as MRI at day 8², time to normal aEEG¹ and peak LDH before 72h⁵ predict long-term outcome with a positive predictive value of 84%, 92% and 80% respectively. Absolute quantification of N-acetyl aspartate in Thalamus and white matter fractional anisotropy using tract based spatial statistics⁴ predict long term outcome. In this study we will continue as a secondary outcome to examine these potential predictors for cooled babies receiving Xenon treatment.

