8.5.4.2 Short term assessment neurological evaluation will include

1. Time to recovery after birth of a normal background aEEG¹
2. MRI scan before 14 days of life^{2,4,35}
3. Peak LDH value within 72h of life^{5,36}
4. First plasma glucose after birth (usually from cord blood)
5. Age in hours after birth when plasma lactate has declined to <5mmol/l
6. Number and type of inotropic drugs needed during stay on the neonatal intensive care unit (typically the period from birth to 3-5 days of age) and the total duration in hours of any inotropic support
7. Number of anticonvulsant drugs given during stay on the neonatal intensive care unit.
8. Amount and duration of sedation (e.g. plasma morphine levels) while ventilated mechanically on the neonatal intensive care unit.
9. Stress levels (saliva, plasma and urinary cortisol and adrenocorticotropic hormone)
10. Age at full oral feeds (breast or bottle or tube)
11. Outcomes of neonatal hearing screening before 14 days of life
12. Clinical examination at birth, at 7 days of age and at discharge including weight and head circumference

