10.0 Data Analysis and Statistical Plan

10.1 Statistical Analysis

This is a prospective randomised comparative outcome study. Data presentation will include descriptive statistics only. These will be compared in the 2 treatment groups but also to recordings of the same variables in a similar group of 45 infants (recruited to cooling only from the same entry criteria) recently treated in our department (historical control data). Differences between the groups will be estimated

Sample size is 26 infants in each group. The advisory statistician for this study is [name] who has also advised on all aspects of the Xenon work (pre-clinical and clinical) undertaken to date.

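### Time from birth to a normal aEEG is left in the between-arm and historical comparisons, although the protocol says xenon itself suppresses the trace

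*Protocol*

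**What the plan says.** Section 3.3, item a, lists "Time to recovery after birth of a normal aEEG" first among the potential predictors of outcome. Section 4.9.2, item 1, repeats it, and section 8.5.4.2, item 1, has "Time to recovery after birth of a normal background aEEG". The same birth-clocked idea stands in the Protocol Summary (secondary objective 1, together with onset of sleep-wake cycling) and, as time to normalisation of background activity, in sections 4.9.1 and 8.5.4.1, item 8 of each.

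The protocol is open about the problem. Section 1.0 reports that in CoolXenon2 "xenon suppresses the aEEG for the entire 18h period of xenon administration and for a short period afterwards". Section 2.3 says that "Xenon in itself depresses the aEEG trace during delivery which means it is unreliable as an early outcome predictor until the treatment has finished", gives the affected period as at least 25 h of age for most infants, and adds that time to a normal trace may or may not be affected. Bayley at 18 months was made the primary outcome.

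On analysis, section 10.1 promises descriptive statistics and says "These will be compared in the 2 treatment groups but also to recordings of the same variables in a similar group of 45 infants"; those infants were cooled only. It adds "Differences between the groups will be estimated". No variable is excepted. On prediction, section 2.3 expects that "we will be able to validate any early predictors in infants cooled early with or without added Xenon", and section 4.9.3.1 will "examine these potential predictors for cooled babies receiving Xenon treatment".

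**The concern.** The clock starts at birth in every infant, but xenon holds down the trace in one arm only. Two infants whose brains recover at the same moment can be given different times because one was breathing xenon. A difference between arms, or between xenon infants and the historical group, then mixes any effect on the brain with an effect on the recording.

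The measure carries weight. Section 1.0 calls it the best single early predictor, and section 4.9.3.1 gives it a positive predictive value of 92% in cooled infants, the highest of the three listed. A later time in the xenon arm would naturally be read as worse recovery. The same shift affects prediction: a given time to normal trace need not mean the same in the two arms, so validation that pools them would blur the relation with 18-month outcome.

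**Working it through.** **Length of the masked period.** Inputs from sections 2.3 and 4.4.2: xenon starts no later than 5 h, runs for 18 h, and recovery takes at least 1 h.

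End of masking = start + 18 + recovery.

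- 5 h start, 1 h recovery: 5 + 18 + 1 = 24 h. The protocol prints at least 25 h, so its own components fall 1 h short.
- 5 h start, 2 h recovery: 5 + 18 + 2 = 25 h, which matches.
- 3 h start, 1 h recovery: 3 + 18 + 1 = 22 h. The 3 h start is an assumption, because no earliest start is stated.

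Neither end is firm: recovery is given as at least 1 h, and elsewhere as a few hours.

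**Direction.** If T is the age at which the trace would have become normal without xenon, s the age at xenon start and w the recovery period, the recorded age in a suppressed infant is

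- T, if T < s (already normal before xenon);
- max(T, s + 18 + w) otherwise.

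Under this rule the recorded age is never earlier than T in the xenon arm, and equals T in control and historical infants.

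**Size, by assumption.** The documents give no distribution of recovery times. Assume T lognormal and identical in both arms (no xenon effect on the brain), log-SD 0.6 or 1.0, s uniform on 3-5 h, every xenon infant suppressed, 26 per arm, 40,000 simulated trials. The median shift is the xenon median with masking minus the median of the same infants without it. Ranges run over the two log-SDs. The last three columns use w = 1 h.

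| Assumed control median (h) | Median shift, w = 1 h | Median shift, w = 2 h | Mean shift (h) | Xenon values delayed | SD of difference in medians (h) |
|---|---|---|---|---|---|
| 12 | 10.8-11.0 | 11.7-11.9 | 7.1-9.2 | 61-82% | 1.8-3.0 |
| 18 | 5.3-5.4 | 6.2-6.3 | 5.7-5.9 | 53-65% | 2.7-4.8 |
| 24 | 1.2-1.9 | 1.7-2.4 | 3.6-4.5 | 45-47% | 4.2-7.4 |
| 36 | 0.0-0.1 | 0.0-0.2 | 1.4-2.9 | 23-31% | 7.4-12.6 |
| 48 | 0.0 | 0.0 | 0.6-1.9 | 11-22% | 9.9-17.0 |

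The SDs in the last column are somewhat small, because masking compresses the xenon values. At a control median of 18 h and log-SD 1.0, the SD without masking is about 6.4 h, against a shift of 5.4 h. Only the 12 h case is clearly outside chance variation at both spreads.

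If 5 of 6 infants are suppressed, the proportion seen in the six healthy pigs of Appendix A4, the median shifts (w = 1 h) are 10.6-10.8, 5.2-5.4, 1.1-1.8, 0.0-0.1 and 0.0 h.

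**Common age.** With suppression over by 25 h, the share normal at 36 h is the same with and without masking. That follows from the model's end point and is not a finding from data.

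**The case against.** Section 10.1 never names aEEG, is descriptive and sets no test. Section 3.3 presents the item as a predictor. The protocol discloses the suppression, confines its warning to aEEG read in the usual way, and moved the primary outcome to Bayley. An analysis plan, not shown here, might add a landmark or an arm term. Materiality is unproven, since the shift runs from 0 to about 11 h on assumption alone.

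Much of this stands. The size is unknown, the protocol does not hide the issue, and its prediction aims already point to looking at xenon infants separately. But the point does not rest on a missing detail. The protocol calls the measure unreliable during and shortly after xenon, keeps it unchanged in six places, and states a comparison rule with no exception. Following that rule gives a confounded difference, descriptive or not.

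Four stronger readings are tempting and are not supported:

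- That the trial's main result is compromised. The Bayley score does not depend on the trace.
- That aEEG should not be timed in xenon infants. Testing it as a predictor there is a stated aim.
- That the artefact can only delay xenon values. That is a property of the model. Section 2.3 also reports that xenon depresses seizures and that fast cessation can bring them on, and the model includes neither.
- That comparison at 36 h is certainly clean. Section 4.7.1 says other sedation is needed once xenon stops, so sedation may still differ by arm.

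**Conclusion.** The concern holds as a confounded secondary comparison that should be corrected. By the protocol's own account, xenon suppresses the trace to at least about 24-25 h of age with a 5 h start, somewhat earlier with an earlier start. The raw difference in time from birth to a normal aEEG, between arms or against the 45 historical infants, therefore includes a drug effect on the recording, expected to run against xenon.

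Its size depends on how many cooling-only infants recover before that age, which the documents do not say. Under the assumed model it is large if the typical control recovers at about 12 h, appreciable but not clearly above chance at 18 h if the spread is wide, small at 24 h, and negligible for medians at 36-48 h, though means still move by 0.6 to 2.9 h.

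**What to change.** 1. Keep recording raw time to normal trace and onset of sleep-wake cycling in all infants, and report them within arm.
2. State in section 10.1 that raw birth-clocked aEEG recovery times are not compared between arms or with the historical infants as a treatment effect. Carry this through the Protocol Summary (secondary objective 1), 3.3 item a, 4.9.1 item 8, 4.9.2 item 1, 8.5.4.1 item 8 and 8.5.4.2 item 1.
3. Compare arms on aEEG background category, already collected as tertiary Endpoint 12 in section 3.4, at one or more prespecified common ages after expected washout. An example is 36 h, with a second age chosen around the 48 h MRI, because the documents do not say whether aEEG continues in the scanner.
4. Flag infants whose xenon ended later than planned. Section 4.6.1 allows xenon to be resumed after a stop and does not say whether lost time is made up. If it were made up in full, 36 h would stay clear for pauses up to 36 - (5 + 18 + 2) = 11 h. Note also that sedation after xenon may differ by arm.
5. Assess prediction of 18-month outcome within arm or with an arm term.

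Cost: no new recording at 36 h, since aEEG already runs until after rewarming. It takes a protocol amendment touching several items, with the approvals in section 12.0. What is given up is between-arm comparison before about 25 h, a period the protocol already treats as unreliable.
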